9.4. Data Sources

This study will utilize the MDV database. The MDV database is a comprehensive resource containing administrative data from over 540 hospitals in Japan, based on hospital claims data and Diagnosis Procedure Combination (DPC) data. This dataset includes information on demographics; mortality; laboratory tests; inpatient (IP), outpatient (OP), and emergency department (ED) claims; treatments; procedures; and costs of approximately 50 million patients, with a significant proportion of these patients being over 65 years old. The MDV database captures approximately 30% of advanced treatment hospitals in Japan, with over one million health claims processed each month. Additionally, the database includes health claim data from all insurance types (Social, National, and Elderly Insurance), providing a comprehensive characterization of patients and treatment paradigms. The MDV database has been used extensively for use in RW evidence generation (14). Studies have used the MDV database to report on the safety of treatments (15), including the safety of dose schedules (16–18), and treatment patterns in oncology (19–21).

Data is available from April 2008 through the most recent data cut. The MDV database is fully de-identified and aggregated. No individual patient can be identified; therefore, informed consent is not required.

9.5. Study Size

The study sample will be identified from secondary data from Japanese hospitals that has already been collected. As the MDV database does not include all Japanese hospitals, the sample will be a convenience sample. The most recent data cut available from MDV will be used for the report. All patients who meet the inclusion/exclusion criteria defined in [Section 9.2](#) will be included in the analyses.

This is a descriptive study with no a priori hypotheses; therefore, formal sample size calculations are not applicable. However, to provide an indication of the expected sample size, the February 2025 data cut, MDV included 128 patients that had at least one hospital claim for elranatamab.

9.6. Data Management

The MDV database, a comprehensive, hospital-based, service-level, all-payer claims database managed by the vendor Medical Data Vision Co., Ltd, will serve as the primary data source for this study. The MDV database includes data from over 540 hospitals and healthcare systems across Japan, encompassing both IP and OP services. It integrates health insurance claims from all insurance types

090177e1a4a71ff1\Approved\Approved On: 05-Nov-2025 14:15 (GMT)

(i.e., Social, National, and Elderly Insurance), providing a comprehensive representative view of RW clinical practice and treatment patterns.

Data will be de-identified prior to transfer from the vendor and monthly updates are being transferred. Data cleaning, transformation, and statistical analyses will be conducted using SAS. Snowflake will be used for secure data storage and preprocessing.

9.7. Data Analysis

All analysis will be descriptive in nature and no formal statistical comparisons will be performed between groups. All characteristics and endpoints will be reported separately for each assessment period and patient exposure groups of interest as defined in [Table 2. Patient Exposure Groups Stratification and Assessment Period for Study Objectives](#).

Raw data transferred by MDV will be reviewed for completeness, consistency and plausibility. Records with missing or implausible values (e.g., negative age, invalid dates) will be flagged and addressed according to predefined rules in the SAP. Duplicate records will be identified and removed. Variables will be derived and categorized as needed for analysis. Diagnosis and procedure codes will be mapped to standardized categories using the International Classification of Diseases, 10th revision (ICD-10) and Healthcare Common Procedure Coding System (HCPCS) classification systems. Missing data will be reported, and no imputation will be performed unless otherwise specified in the SAP.

Detailed methodology for summary and statistical analyses of data collected in this study will be documented in a SAP, which will be dated, filed, and maintained by the sponsor. The SAP may modify the plans outlined in the protocol; any major modifications of primary endpoint definitions or their analyses would be reflected in a protocol amendment.

9.7.1. Descriptive Analysis

Dichotomous and categorical variables will be summarized by the number and percentage of patients in each category. Continuous variables will be described using mean, standard deviation (SD), median, interquartile range (IQR), minimum, and maximum. If applicable, the frequency and percentage of patients with missing data for each variable will be described. For reporting conventions, mean, median, and SD will be rounded to 1 decimal place. Percentages will be rounded to 1 decimal place.

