Duration of treatment, patient level	Outcome	MDV	Days between first and last treatment administration for elranatamab (continuous)	Follow-up period
Duration of treatment, claim level	Outcome	MDV	Total calendar duration of elranatamb observation in days, and the date of the first observed elrantatamab claim	Follow-up period
Only 44mg/1.1mL vials [Summary statistic]	Outcome	MDV	Number of patients with only 44mg/1.1mL vials during the time period (yes/no)	Follow-up period
Only 76mg/1.9mL vials [Summary statistic]	Outcome	MDV	Number of patients with only 76mg/1.9mL vials during the time period (yes/no)	Follow-up period
Relative Administration Intensity (RAI) [Summary statistic]	Outcome	MDV	Ratio of the elranatamab administrations received divided by the expected number of administrations according to the Japan elranatamab label See Section 9.7.4 for more details	Follow-up period

Abbreviations: mL: millilitre; mg: milligram; RAI: Relative Administration Intensity; SUD: step-up dosing.

Table 5. Variables for Outcomes (Objective 3 – HCRU and Costs)

090177e1a4a71ff1\Approved\Approved On: 05-Nov-2025 14:15 (GMT)

Variable	Role	Data Source	Operational Definition	
			Definition	Assessment Period(s)
IP claim [Summary statistic]	Outcome	MDV	Number of patients with ≥ 1 all-cause IP claim (yes/no)	HCRU baseline period SUD period Follow-up period (overall only)
			Number of all-cause IP claims PPPM. Reported for all patients and for patients with ≥ 1 all-cause IP claim.	HCRU baseline period Follow-up period (overall only)
			Number of all-cause IP claims PPPD. Reported for all patients and for patients with ≥ 1 all-cause IP claim.	SUD period
OP claim [Summary statistic]	Outcome	MDV	Number of patients with ≥ 1 all-cause OP claim (yes/no)	HCRU baseline period SUD period Follow-up period (overall only)
			Number of all-cause OP claims PPPM. Reported for all patients and for patients with ≥ 1 all-cause OP claim.	HCRU baseline period Follow-up period (overall only)
			Number of all-cause OP claims PPPD. Reported for all patients and for patients with ≥ 1 all-cause OP claim.	SUD period

090177e1a4a71ff1\Approved\Approved On: 05-Nov-2025 14:15 (GMT)

Variable	Role	Data Source	Operational Definition	
			Definition	Assessment Period(s)
ED claim [Summary statistic]	Outcome	MDV	Number of patients with ≥ 1 all-cause ED claim (yes/no)	HCRU baseline period SUD period Follow-up period (overall only)

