9.7.3. Relative Administration Intensity

RAI will be calculated as the cumulative frequency of administration received over the expected number of administrations. Since response is needed to determine if switching to bi-weekly doses is appropriate and is not available in MDV, two schedule definitions will be used to estimate the expected number of administration to calculate RAI (Table 10. Dosing Schedule of Elranatamab during Follow-up Period for Patients Switching to

Q2W and Table 11. Dosing Schedule of Elranatamab during Follow-up Period for Patients staying on

QW Table 10. Dosing Schedule of Elranatamab during Follow-up Period for Patients Switching to

Q2W).

$$\text{RAI} = \frac{\text{Number of administrations received}}{\text{Number of expected administrations during the time period}}$$

a) Schedule 1¹

Assumption that all patients switch to bi-weekly doses (Q2W) after day 169 post-index.

Table 10. Dosing Schedule of Elranatamab during Follow-up Period for Patients Switching to Q2W

Follow-up Sub-Periods	Expected Administrations	Vial Size
Index date - Day 8	3 administrations	2 x 44mg/1.1mL 1 x 76mg/1.9mL
Day 9 - Day 168	1 administration per week	76mg/1.9mL
Day 169 – End of follow-up	1 administration every two weeks	76mg/1.9mL

Notes:

090177e1a4a71ff1\Approved\Approved On: 05-Nov-2025 14:15 (GMT)

¹ Adapted from dosing and administration guidance of the Japanese elranatamab label available at <https://labeling.pfizer.com/ShowLabeling.aspx?id=20462>

b) Schedule 2¹

Assumption that all patients continue with weekly doses (QW) after day 169 post-index.

Table 11. Dosing Schedule of Elranatamab during Follow-up Period for Patients staying on QW

Follow-up Sub-Periods	Expected Administrations	Vial Size
Index date - Day 8	3 administrations	2 x 44mg/1.1mL 1 x 76mg/1.9mL
Day 9 – End of follow-up	1 administration per week	76mg/1.9mL

Notes:

¹ Adapted from dosing and administration guidance of the Japanese elranatamab label available at <https://labeling.pfizer.com/ShowLabeling.aspx?id=20462>

Treatment exposure will be assessed across the different follow-up periods. End of follow-up is defined as the end of the hospital claim of the last elranatamab administration inclusive.

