9.7.4. Healthcare Resource Utilization and Costs

All-cause HCRU will be measured as the total number IP, OP, and ED that occurred over the follow-up period. Health claims will only be counted once per day to estimate visits. Additionally, the total length of IP stays will be reported among patients with at least one IP visit. Costs will be adjusted for inflation. More details will be provided in the SAP.

PPPM

PPPM standardizes HCRU and cost by calculating the average of a specific variable or a number of specific events (e.g., ED health claims, IP health claims) per month for each patient. In this study, PPPM will be used to report ED, IP and OP visits and cost for the HCRU baseline period and the follow-up period. To obtain PPPM, the following formula will be used for each patient:

$$PPPM = \frac{\text{Total number of events during a specified period}}{\text{Duration of the specified period (in months)}}$$

PPPD

PPPD standardizes HCRU and cost by calculating the average of a specific variable or a number of specific events (e.g., ED health claims, IP health claims) per day for each patient. In this study, PPPD

090177e1a4a71ff1\Approved\Approved On: 05-Nov-2025 14:15 (GMT)

will be used to report ED, IP and OP visits and cost for the SUD period. To obtain PPPD, the following formula will be used for each patient:

$$PPPD = \frac{\text{Total number of events during a specified period}}{\text{Duration of the specified period (in days)}}$$

This calculation will allow meaningful comparisons across patients with varying assessment period lengths, by normalizing resources use to a monthly rate. Summary statistics (mean, median, min, max) will then be reported to understand average monthly cost and utilization patterns across patients.

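### One decimal place for every mean, median and SD prints infrequent per-day visit rates as 0.0 and makes relative administration intensity coarse

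*Protocol*

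**What the plan says.** Section 9.7.1 (Descriptive Analysis) lists the summaries for continuous variables and then fixes their format: "For reporting conventions, mean, median, and SD will be rounded to 1 decimal place". It adds "Percentages will be rounded to 1 decimal place". The rule does not mention the IQR, minimum or maximum, and it exempts no variable.

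Two families of variables fall under it:

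- **RAI**, an Objective 2 (primary) outcome. Table 4 defines it as "Ratio of the elranatamab administrations received divided by the expected number of administrations according to the Japan elranatamab label". Section 9.7.3 repeats this: "RAI will be calculated as the cumulative frequency of administration received over the expected number of administrations". The result is a plain ratio, not multiplied by 100. Tables 10 and 11 expect "3 administrations" from index to day 8, then "1 administration per week". From day 169, Schedule 1 changes to "1 administration every two weeks".
- **PPPD**, an Objective 3 measure. Section 9.7.4 divides events by days and says that it "will be used to report ED, IP and OP visits and cost for the SUD period". The same section counts claims at most once a day. Table 5 asks for each visit rate both in all patients and in patients with at least one such claim.

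Section 9.8 commits the analysts to following the protocol strictly. Section 9.7 allows the SAP to modify the protocol's plans.

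**The concern.** One decimal suits ages, days and percentages. It suits poorly a per-day visit rate, which cannot much exceed 1 for one visit type and is small when visits are rare, and a ratio in which one weekly dose is worth about 0.04. If the table formats follow the rule, a planned all-patient visit rate can appear as zero, sometimes with a zero SD, in SUD groups where visits took place. Groups with quite different rates would then look identical. For RAI, a mean shortfall of about one dose over five months would not show.

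This is a rule the protocol states, not a detail it leaves open, so it can be judged as written.

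**Working it through.** The protocol gives no figure to reproduce here, so this is direct arithmetic followed by rounding to one decimal (halves rounded up).

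**Length of the SUD period.** The period includes both end dates. Tables 10 and 11 place all three step-up administrations within days 1 to 8, so 8 days is the scheduled length. In Table 12, Group A has two intervals of 1 to 7 days: 1 + 1 + 1 = 3 days up to 7 + 7 + 1 = 15 days. Group B has one or both intervals of 8 to 14 days: 8 + 1 + 1 = 10 days up to 14 + 14 + 1 = 29 days.

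**Visit PPPD for one patient.** One visit over L days gives 1/L:

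| L (days) | 1/L | prints |
|---|---|---|
| 8 | 0.125 | 0.1 |
| 15 | 0.067 | 0.1 |
| 21 | 0.048 | 0.0 |
| 29 | 0.034 | 0.0 |

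**Visit PPPD mean over all patients.** The documents give no visit frequencies. *Assumption:* a share p of patients has exactly one visit, and all have the same L. Then mean = p/L and SD = sqrt(p(1 − p))/L.

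| p | L = 8: mean (prints) | L = 8: SD (prints) | L = 15: mean (prints) | L = 15: SD (prints) |
|---|---|---|---|---|
| 5% | 0.006 (0.0) | 0.027 (0.0) | 0.003 (0.0) | 0.015 (0.0) |
| 10% | 0.0125 (0.0) | 0.0375 (0.0) | 0.007 (0.0) | 0.020 (0.0) |
| 20% | 0.025 (0.0) | 0.050 (0.1) | 0.013 (0.0) | 0.027 (0.0) |
| 30% | 0.0375 (0.0) | 0.057 (0.1) | 0.020 (0.0) | 0.031 (0.0) |
| 50% | 0.0625 (0.1) | 0.0625 (0.1) | 0.033 (0.0) | 0.033 (0.0) |

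The mean first prints 0.1 when p/L reaches 0.05. That needs p = 0.05 × 8 = 40% at 8 days, or p = 0.05 × 15 = 75% at 15 days. With fewer than 25% of patients having a visit, the median and both quartiles are 0, so the mean is the only central summary that carries the rate.

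**PPPM, for comparison.** The 180-day baseline is 180/30.44 = 5.9 months. One visit per user prints a mean of 0.0 unless about 0.05 × 5.9 = 30% of patients have one. The problem is the same but milder.

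**RAI.** Days 9 to 168 are 160 days, so 160/7 = 22.9 administrations are expected. One administration is worth 7/160 = 0.044, and a printed step of 0.1 spans 0.1 × 22.9 = 2.3 administrations.

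| Mean doses missed | RAI | prints |
|---|---|---|
| 0 | 1.000 | 1.0 |
| 1 | 0.956 | 1.0 |
| 2 | 0.913 | 0.9 |
| 3 | 0.869 | 0.9 |
| 4 | 0.825 | 0.8 |
| 5 | 0.781 | 0.8 |

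Rounding can move a reported value by up to 0.05, which is 0.05 × 22.9 = 1.1 weekly administrations. In days 1 to 8, where three are expected, 0, 1/3, 2/3 and 1 print as 0.0, 0.3, 0.7 and 1.0 and stay distinct. The contrast between schedules also survives. At day 365, Schedule 1 expects 3 + 160/7 + 197/14 = 39.9 and Schedule 2 expects 3 + 357/7 = 54. A patient fully dosed on Schedule 1 therefore has RAI 1.0 under one schedule and 39.9/54 = 0.74 (prints 0.7) under the other.

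**The case against.** The strongest reply is that this is a display format, normally settled in the SAP and table shells, and that the information survives elsewhere.

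- **Other rows.** Table 5 also reports the number of patients with at least one claim of each type, and Section 9.7.1 adds the percentage. A 10% share with an emergency visit would appear as 10.0%. This stands: the occurrence of visits is not hidden. The planned all-patient rate itself still prints 0.0.
- **RAI has a companion.** Table 4 asks for mean days between claims. Over 160 days, 0, 1, 2 and 3 missed doses imply mean intervals of about 7.0, 7.3, 7.7 and 8.1 days, all distinct at one decimal. This stands too and limits the harm, but it does not make the RAI row itself finer.
- **Costs and frequent visits.** Cost per day is a sum of money and loses nothing that matters. Visits on 6 of 8 days give 0.75 (prints 0.8). If inpatient days are what is counted, a patient hospitalised throughout has a rate near 1.0. Inpatient rows therefore need not be affected.
- **The SAP may override.** True. But nothing in the protocol signals an exception, and Section 9.8 promises strict adherence.

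A reader might go further and infer that the rule erases RAI and per-day resource use altogether, or that every step-up row would print 0.0 or the same 0.1 in each SUD group. The documents do not support that. RAI varies over tenths, from 0 to about 1, and larger shortfalls remain visible. The collapse to 0.0 concerns infrequent visit types only.

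**Conclusion.** The rule is badly fixed for two scales. For infrequent visit types in the SUD period, the all-patient PPPD mean prints 0.0 although events occurred, unless 40% (8 days) or 75% (15 days) of patients have a visit. At 5% to 10% over 8 days the SD prints 0.0 as well. RAI is coarsened by up to 0.05, so in days 9 to 168 mean shortfalls of 0 and 1 dose look alike, as do 2 and 3.

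The PPPD figures rest on assumed visit shares, one visit per user and a common period length, because the protocol gives no visit rates. The RAI figures follow from Tables 10 and 11 alone. The effect is on reporting only: no data, derivation or comparison is lost, and the SAP could also correct it.

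**What to change.** Replace the rounding sentence in Section 9.7.1 with decimals set by variable:

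- one decimal for days, months, years and percentages;
- at least two decimals for RAI, or RAI as a percentage with one decimal;
- at least three decimals for visit PPPD, or visits per 100 patient-days.

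Two decimals for PPPM visit counts is a reasonable companion change.

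With this, 0, 1, 2 and 3 missed doses in days 9 to 168 read 1.00, 0.96, 0.91 and 0.87. Visit shares of 5%, 10%, 20% and 30% over 8 days read 0.006, 0.013, 0.025 and 0.038 instead of four zeros. The cost is one sentence and the table formats, with no new data or analysis. It should be done before the tables for the final report are produced.

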9.7.2. Incidence and prevalence calculations

The incidence of CRS, ICANS, and cytopenias will be determined by counting the number of new cases that arise within a specified time frame, divided by the population at risk during that period. An incident case is defined as a new occurrence of the condition following a 30-day washout period, during which no previous cases are considered. The prevalence of CRS, ICANS, and cytopenia will be calculated by counting the total number of cases (both new and existing) present in the population at a specific point in time, divided by the total population size.

Similarly, the incidence of infections will be calculated by counting the number of new cases that arise within a specified time frame, with a 60-day washout period applied to define new cases. The prevalence of infections will be calculated by counting the total number of infection cases present in the population at a specific point in time, divided by the total population size.

$$\text{Incidence Rate} = \frac{\text{Number of new cases}}{\text{Population at risk}} * \text{Population size}$$

$$\text{Prevalence Rate} = \frac{\text{Number of cases}}{\text{Total population}} * 100$$

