8. RESEARCH QUESTIONS AND OBJECTIVES

Research Question: What are the characteristics of adult patients with MM who initiate elranatamab in Japan, and the SUD process, treatment patterns, HCRU, and safety associated with elranatamab administration?

The following objectives will be assessed among patients with MM receiving elranatamab:

Primary objectives:

- Objective 1: To describe patients with MM initiating elranatamab, including demographics, treatment and medical history.
- Objective 2: To describe and characterize elranatamab utilization, including timing, administration and dosing, during the follow-up period, including the step-up dosing (SUD) period.

Secondary objectives:

- Objective 3: To describe HCRU and costs associated with elranatamab usage during the follow-up period, including the SUD period.
- Objective 4: To describe the use of other treatments for MM including supportive therapy during the follow-up period.
- Objective 5: To describe incidence and prevalence of cytokine release syndrome (CRS), immune effector cell associated neurotoxicity syndrome (ICANS), and cytopenias during the SUD period.
- Objective 6: To describe infection incidence and prevalence during the follow-up period.

Exploratory objectives:

- Exploratory Objective 1: To describe the use of supportive medications during the SUD period and administration of IVIG within the 30-day post-index period.

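### Section 9.7.2 multiplies incidence by population size, so the result depends on group size, and it gives infections no time denominator although follow-up varies

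*Protocol*

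**What the plan says.** Section 9.7.2 describes the incidence of CRS, ICANS and cytopenias as "counting the number of new cases that arise within a specified time frame, divided by the population at risk during that period", with a 30-day washout. For infections, "the incidence of infections will be calculated by counting the number of new cases that arise within a specified time frame", with a 60-day washout; that sentence names no denominator. One formula, labelled a rate, then serves for incidence, with new cases as numerator and, as denominator and multiplier, "Population at risk}} * \text{Population size". The prevalence formula directly below uses a fixed scale, "Number of cases}}{\text{Total population}} * 100", and the text counts prevalent cases "present in the population at a specific point in time, divided by the total population size".

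Table 2 assigns Objective 5 to Group A, Group A+B and Group C. CRS and ICANS use a 14-day window and cytopenias use the SUD period. Objective 6 is "To describe infection incidence and prevalence during the follow-up period". Table 2 assigns it to the study population only, at the index date, over days 1 to 8, days 9 to 168 and day 169 onward, and overall. Section 9.7.5 repeats Objectives 5 and 6 in low-weight patients.

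**The concern.** The words and the formula in Section 9.7.2 do not agree. The words give a proportion. The formula multiplies that proportion by a quantity which, on the section's own usage ("divided by the total population size"), is the number of patients. The output then moves with the size of the group being reported.

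The second problem is time. Follow-up runs from the index date to the end of each patient's last elranatamab claim, so its length differs between patients. Neither the definition nor the formula contains person-time, although the result is called a rate. An infection figure built this way mixes how often infections occur with how long patients were observed.

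The third is that prevalence is worded as a point measure, while Tables 7 and 8 mostly assess it over windows.

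Objectives 5 and 6 carry the safety results of a study that Section 7 designates a PASS, and a reader would take the printed rates at face value.

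**Working it through.** The protocol states no numerical incidence, so there is no figure to reproduce. The risks, case counts and hazards below are assumptions for illustration. The 128 patients come from Section 9.5 (February 2025 data cut).

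**1. What the formula returns.** Let c be new cases, R patients at risk and N population size. The formula is c / R × N.
- If R = N, it reduces to c, the observed number of cases.
- If the washout removes patients, it is c × (N / R), a count scaled up to the whole group. With c = 60, R = 120, N = 128: 60 / 120 × 128 = 64. Only 60 cases occurred, and the risk is 60 / 120 = 50.0%.

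**2. Group size.** With everyone at risk and a 50% risk, N = 80 gives 40 / 80 × 80 = 40 and N = 20 gives 10 / 20 × 20 = 10. At a 30% risk, N = 20, 64 and 128 give 6.0, 19.2 and 38.4; a fixed multiplier of 100 gives 30.0 each time. Because A+B contains A, with everyone at risk the formula can never give A+B a lower figure than A, even if Group B had no events.

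**3. Follow-up length (infections).** With a constant hazard h per month, the proportion with a first infection by t months is 1 − exp(−h t):

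| h per month | 1 month | 3 months | 6 months | 12 months |
|---|---|---|---|---|
| 0.05 | 4.9% | 13.9% | 25.9% | 45.1% |
| 0.10 | 9.5% | 25.9% | 45.1% | 69.9% |
| 0.20 | 18.1% | 45.1% | 69.9% | 90.9% |

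At h = 0.10 and N = 128 the printed formula gives 12.2, 33.2, 57.8 and 89.4.

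**4. Sub-periods.** Days 1 to 8 last 8 days and days 9 to 168 last 160 days. Fully observed, with 30.44 days per month and h = 0.10, the proportions are 1 − exp(−0.10 × 8 / 30.44) = 2.6% and 1 − exp(−0.10 × 160 / 30.44) = 40.9%, purely from window length. For h = 0.05 they are 1.3% and 23.1%; for h = 0.20, 5.1% and 65.0%. Day 169 onward has no fixed end. Section 9.3.1 also includes patients whose follow-up ends inside a sub-period, so time at risk varies even in the bounded ones.

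**5. With person-time.** Expected time to first infection or end of observation is (1 − exp(−h t)) / h. Dividing the expected proportion by this returns h: at h = 0.10, 10.0 first infections per 100 patient-months at 1, 3, 6 and 12 months alike.

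**6. The plan's own precedent.** Section 9.7.4 divides HCRU and costs by period length because assessment periods differ between patients. Section 9.7.2 has no counterpart.

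**The case against.** The multiplier may be a loosely worded reporting base, such as per 100 or per 1,000. That is possible, but no base is stated and the section uses the term for the number of patients. A fixed base would cure the group-size fault and leave the missing time denominator.

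The correct proportion will probably be visible anyway. Tables 7 and 8 code events as Yes/No, and Section 9.7.1 summarises such variables by number and percentage. This stands and limits the harm: a reader would see n (%) beside a mis-scaled rate.

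A proportion over a named window is also a legitimate descriptive measure. For CRS and ICANS in 14 days this is right. For infections, the sub-periods, time to first infection and days between infections help, but do not remove the dependence on observation time shown above.

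Several stronger readings are tempting and not supported:
- That the formula always returns the observed case count. It does so only when every patient is at risk.
- That infection figures are distorted between Groups A, A+B and C. Table 2 reports infections for the study population only. For Objective 6, the group-size effect arises in comparing the low-weight subgroup with the whole population.
- That infection figures rise in strict proportion to follow-up. They do not if each patient counts once.
- That point prevalence is never workable. Table 2 lists the index date for infections.

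The SAP may modify secondary analyses under Section 9.7. That does not make the printed formula right, and Section 9.8 says the protocol will be strictly followed.

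**Conclusion.** The incidence formula is wrong as printed: it contradicts the definition in its own section, and nothing else in the protocol corrects it. For Objective 5, and in the low-weight subgroup, equal risks give different figures through group size alone. For Objective 6, the lack of a time denominator makes the figure depend on length of observation: 45.1% to 90.9% infected at 12 months for assumed hazards of 0.05 to 0.20 per month, against 4.9% to 18.1% at 1 month. The direction of both effects follows from the definitions; their size rests on the assumed risks and a constant hazard. The prevalence point is one of wording. The consequence is confined to how secondary descriptive safety results are reported and read. The study plans no hypothesis tests or formal group comparisons, so none is affected.

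**What to change.** Change Section 9.7.2 and carry the change into the SAP:

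- **CRS, ICANS, cytopenias:** cumulative incidence (%) = patients with a first new event / patients at risk at the start of the window × 100. The SUD period varies in length, so read the cytopenia figure with the SUD durations that Table 4 already reports.
- **Infections:** keep n (%) and add an incidence rate = new infections after the 60-day washout / person-time at risk, per 100 patient-months or patient-years, by sub-period and overall.
- **Prevalence:** label it period prevalence over the named window, and keep point prevalence only where a date is named.

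The cost is small. The dates that define follow-up are already needed for the planned analyses. The one real addition is a rule for repeat infections and for how the washout affects time at risk. Confidence intervals would be useful but are optional and not part of the correction.
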